#### **4.4.6 Other missing values**

Other missing values will not be imputed. Frequency tables for categorical data will include the number of missing values as additional categories. Percentages will be calculated as proportion of each category including the category of missing values.

## **4.5 Interim analyses and data monitoring**

### **4.5.1 Interim and final post market surveillance report**

Bayer will submit an Interim Postmarket Surveillance Report every 6 months for the first 2 years of the postmarket surveillance and annually, thereafter, from the date of approval of the 522 postmarket surveillance study plan which was anticipated to be on September 4, 2016.

Per FDA's final guidance document on Postmarket Surveillance issued on May 16, 2016 (located at <http://www.fda.gov/downloads/MedicalDevices/DeviceRegulationandGuidance/GuidanceDocuments/ucm268141.pdf>), after approval of the study plan, FDA may post surveillance plan parameters related to the study design and objectives on the FDA postmarket surveillance webpage (<http://www.accessdata.fda.gov/scripts/cdrh/cfdocs/cfPMA/pss.cfm>). Furthermore, the FDA may post the following information from interim postmarket surveillance reports in the following conditions:

- Number of study sites enrolled (to be updated after submission of each interim report).
- Number of patients enrolled (to be updated after submission of each interim report).
- Interim summary data and/or analyses thereof when appropriate to protect the public health, for example when interim results raise safety concerns or may otherwise impact treatment.
- Interim summary data and/or analyses thereof when statistically and methodologically appropriate and mutually agreed upon by FDA and Bayer, to be negotiated at such time.

The final post market surveillance report will be submitted no later than three months after postmarket surveillance study completion (as defined by database lock).

When recruitment is finalized, the Propensity Score (PS) development will start. For this purpose, an outcome-blinded party independent to the conduct of the study will receive all baseline data of subjects together with their initial treatment allocation (at index).

The independent party will generate a proposal to proceed on the basis of the data available. This will also include assessments on the overlap of the PS density functions for the treatments, and its impact on the adequacy of analyses planned. The generation of the score will be documented with all decisions taken (variables selected for inclusion in the model, procedures to achieve balance, (matching procedures (caliper distance) and final model).

This proposal will subsequently be discussed with the FDA.

### **4.5.2 Data monitoring**

A DMC will be assembled at the beginning of the study. The DMC members will be independent of the sponsor and have no serious conflict of interest. The roles and responsibilities are defined in the DMC Charter.

## **4.6 Data rules**

Medical texts and device events will be coded with the most recent MedDRA version while concomitant medication will be coded by the WHO drug dictionary.

Concomitant medication comprises all medications which started on or after the index date as well as all medications which begun before the index date with a stop date after the index date or still ongoing at end of study.

#### **4.6.1 Baseline**

Baseline is generally defined as the last available value at or before the index event.

#### **4.6.2 Subject validity**

A subject will be entirely excluded from all analyses if

- she has not signed the informed consent form,

Data of subjects withdrawing their consent for further study participation will be used up to the date of withdrawal.

#### **4.6.3 Visit labels**

##### **General Rules**

For all the variables analyzed by visits, the values at scheduled visits will be used if available. If values at scheduled visits are missing but values are available at an associated unscheduled visit, the value from the closest unscheduled visit will be used to the scheduled visit.

If there are no values at scheduled or unscheduled visits, it will be considered as missing.

A value from the discontinuation visit (for discontinued subjects) will be assigned to the next scheduled visit (for the particular assessment per protocol) after the last visit the subject has completed.

##### **Rules for subjects who have a second placement attempt**

For subjects who have a second placement procedure performed and data are available based on both placement procedures, all study assessments should be performed for the second placement and the analysis will be based on the scheduled visits for the second placement for the summary purpose. Unless otherwise specified. Particularly, the following rules are applied:

- After the second placement procedure, the 1-week post-procedure telephone contact assessments should be repeated at 1 week after the second placement procedure. If the second placement procedure is performed before the 1-week post-procedure telephone contact, then the 1-week contact should be performed only once, at 1 week after the second placement procedure.
- If the second placement procedure occurs on or after the 3-month telephone contact, then the 3-month post-procedure assessments should be repeated at 3 months after the second placement procedure.

- If the second placement procedure occurs before the 3-month telephone contact, then the 3-month telephone contact should be rescheduled to occur at 3 months after the second placement procedure only.
- All other post-procedure visits will continue to be scheduled based on the date of the first placement procedure (ie, 12, 24, and 36 months post-procedure).

**For the PRO evaluations:**

PROMIS 3a and 8a:

- After the second placement procedure, PRO evaluations for Week 1, 2, 3, and 4 and Month 2 and 3 should be repeated based upon the date of the second placement procedure.
- Evaluations at Month 6 through Month 36 will continue to be scheduled based on the first placement procedure date.

AMSS – all evaluations will be based on the first placement procedure.

SF-36 – all evaluations will be based on the first placement procedure.

## **5 Analysis sets**

### **5.1 Assignment of analysis sets**

The goal of this study is to assess the various aspects of safety of the procedures studied. Assuming there is adequate overlap in the PS distribution to enable comparisons in the PS confounder-adjusted population between treatment groups, the adjusted full analysis set will be the primary analysis set.

#### **Safety analysis set**

A subject will be included in the safety analysis set if the subject came to the sterilization procedure visit.

#### **Full analysis set**

A subject will be included in the full analysis set (FAS) if she has selected a treatment and, at the time of the procedure, an Essure device has been introduced into the hysteroscope or has an incision/puncture for laparoscopy.

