## **2 Study objectives**

The study has the following objectives:

- To evaluate the proportion of subjects who experience new onset or worsening chronic lower abdominal and / or pelvic pain who have undergone Essure placement (anyone who has had an attempt at placement defined as an insert that was placed in the operating channel of the hysteroscope will be included in the analysis, regardless of whether or not they are relying on Essure for contraception) compared to the proportion of subjects who had an attempt at laparoscopic tubal sterilization (defined as anyone who has had an incision or puncture of the skin, regardless of whether or not sterilization was successfully completed), and to better characterize these reported outcomes and identify pre-procedural and procedure-related characteristics that may be related to their occurrence.
- To evaluate the proportion of subjects who experience new onset or worsening abnormal uterine bleeding who have undergone Essure placement (as defined above) compared to the proportion of subjects who have undergone laparoscopic tubal sterilization (as defined above)

and to better characterize these reported outcomes and identify pre-procedural and procedure-related characteristics that may be related to their occurrence.

- To evaluate the proportion of subjects who undergo gynecologic or related surgical intervention (including “insert removal” and hysterectomy) after undergoing hysteroscopic sterilization with Essure versus laparoscopic tubal sterilization.
- To identify the proportion of subjects who experience new onset or worsening allergic, hypersensitivity, or autoimmune-like reactions after Essure placement or laparoscopic tubal sterilization and to better characterize these reported outcomes and any characteristics that may be related to their occurrence.
- To collect data on patient reported outcomes in subjects who have undergone hysteroscopic or laparoscopic tubal sterilization procedures.
- To collect rates of adverse events (AEs) in subjects undergoing Essure placement or laparoscopic tubal sterilization

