### Laparoscopic tubal sterilization

- Subjects who initially attempted the laparoscopic tubal sterilization procedure

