Additional Endpoints	
 
New exposure to metals including new cosmetic or medical permanent implants and/or piercings and its material, wear eyeglasses
 
Change from baseline to 1 Year in serum or plasma nickel level, titanium level— both categorical and continuous forms, association with adjudicated hypersensitivity/allergic/autoimmune events
 
Change from baseline to 1 Year in serum or plasma nickel level, titanium level association with adjudicated hypersensitivity/allergic/autoimmune events
 
Proportion of women who crossed over to alternate sterilization method (e.g., Essure subjects who attempted laparoscopic tubal sterilization)
 

Essure Insert Placement Procedure a	Type of hysteroscopy procedure, reason for second attempt, facility where procedure was performed, premedication, pregnancy test performed within 24 hours of this procedure, hormonal manipulation to promote atrophic or proliferate endometrium, anesthesia used, type of anesthesia used, placement technique, hysteroscopy possible, retroverted uterus, distention medium used, type of distention medium, duration of procedure, Essure procedure attempted, reason Essure procedure not attempted, experienced

	Endpoint/Variable
	AE during hysteroscopy, placement status (by tube), ostium in the field of vision during placement (by tube), if successful - number of Essure trailing coils, number of inserts used (by tube), device type, reasons for unsuccessful placement (by tube), primary reason for unsuccessful placement (by tube), first line confirmation test to be performed, investigator's rating of ease of use of the Essure device, physician's rating of procedure difficulty, experienced AE during Essure implant procedure, Primary method of contraception used just prior to procedure, Primary method of contraception used until reliance assessment, additional procedures performed in conjunction with the Essure procedure
Transvaginal Ultrasound a	Reason for TVU, facility where TVU performed, uterine position at time of TVU, insert detected (by tube), implant location (by tube), reason for unsatisfactory placement (by tube), TVU results satisfactory to allow the subject to rely on Essure, individual who performed TVU, individual who interpreted TVU, physician's rating of procedure difficulty, experienced AE during TVU

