**Table 4 - Search list for invasive gynecologic surgery**

Terms
Endometrial Ablation
Hysterectomy; subtotal (only uterus removed)
Hysterectomy; Total (uterus and cervix removed)
Hysterectomy; Radical (uterus, cervix, ovaries, oviducts, lymph nodes, & lymph channels removed)
Unilateral/bilateral Salpingectomy(excision of the fallopian tube)
Partial Salpingectomy
Unilateral/bilateral Oophorectomy (excision of the ovary) or removal of the ovarian cyst
Unilateral/bilateral salpingoophorectomy (excision of the ovary and fallopian tube)
Cornual resection
Diagnostic laparoscopy
Salpingotomy
Operative hysteroscopy and specify
Surgery for vascular injury, specify
Surgery for visceral organ injury, specify

Besides all these items from additional pelvic/abdominal surgery eCRF, the following situations will also be considered as invasive gynecologic surgery.

If a subject had Essure removal using Salpingectomy, Hysterectomy and Cornual resection, she will be considered as having invasive gynecologic surgery and classified as “Essure removal using invasive gynecologic surgery”. If a subject had laparoscopic tubal sterilization after she had Essure attempt, she will be considered as having invasive gynecologic surgery and classified as “laparoscopic tubal sterilization after Essure attempt”. If a subject had Essure attempt after she had laparoscopic tubal sterilization, she will be considered as having invasive gynecologic surgery and classified as “operative hysteroscopy, Essure placement after laparoscopic tubal sterilization”.

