#### **6.6.2 Analysis based on different analysis set**

All the baseline characteristics defined in [Table 1](#), main endpoints variables defined in [Table 2](#), and summary AEs will be analyzed using full analysis set, adjusted full analysis set, reliance set and adjusted reliance set with adjusted full analysis set being the primary analysis.

Descriptive analyses of the PRO questionnaires will be done using full analysis set, adjusted full analysis set, reliance set and adjusted reliance set with adjusted full analysis set being the primary analysis.

For other outcome variables listed in [Table 2](#) and AEs by PT and SOC, the analysis will be conducted using the full analysis set and adjusted full analysis set.

For device events, the analysis will be conducted based the full analysis set using all the data till the end of study.

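### Harms and failures of a hysteroscopy stopped before an insert is loaded have no assured place in any adverse event rate by group, because every AE table uses the FAS or its subsets and none uses the Safety Analysis Set

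*SAP*

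**What the plan says.** **Entry to the FAS.** SAP 5.1 (repeated in protocol 10.2) requires that "an Essure device has been introduced into the hysteroscope or has an incision/puncture for laparoscopy". The objectives in SAP 2 and protocol 4 use the same thresholds. For Essure there must be "an attempt at placement defined as an insert that was placed in the operating channel of the hysteroscope"; an LTS attempt is "defined as anyone who has had an incision or puncture of the skin, regardless of whether or not sterilization was successfully completed".

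**Safety Analysis Set.** A woman belongs to it "if the subject came to the sterilization procedure visit". It is the only defined set that keeps women whose procedure stopped before the FAS threshold.

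**Which set serves which table.** SAP 6.6.2 puts the main endpoints and summary AEs on the FAS, adjusted FAS, reliance and adjusted reliance sets. For the other Table 2 variables and AEs by PT and SOC, "the analysis will be conducted using the full analysis set and adjusted full analysis set". Device events use the FAS. The Safety Analysis Set is given nothing. SAP 6.6.1 mentions an adjusted safety analysis set that is never defined, and protocol 9.6.1.1 uses a safety population only for cytokine summaries.

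**Data collected.** SAP Table 2 includes whether hysteroscopy was possible, whether the Essure procedure was attempted, "reason Essure procedure not attempted", and AEs during hysteroscopy. SAP 6.5.1 tabulates AEs related to hysteroscopy separately from AEs related to Essure placement.

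**Grouping.** SAP 5.2 groups by first attempt; the LTS group is "Subjects who initially attempted the laparoscopic tubal sterilization procedure". For the surgery endpoint, the text after Table 4 says: "If a subject had laparoscopic tubal sterilization after she had Essure attempt, she will be considered as having invasive gynecologic surgery".

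**The concern.** The two entry points are not parallel. An LTS woman counts from the first incision or puncture. A woman who chose Essure can have anesthesia, dilation, scope entry and distension, and can be injured or have the procedure abandoned, without an insert ever reaching the channel. The sponsor foresaw this case, because the data collection describes it. The analysis plan then filters it out: in the FAS, the reason an Essure procedure was not attempted is empty or nearly so by construction.

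The objectives include AE rates by procedure, and perforation by any surgical instrument is an AE of special interest (protocol 9.6.1.1). A regulator reading the hysteroscopy-related AE table would reasonably assume that it covers every hysteroscopy begun for sterilization. It does not. The treatment of women who go from a failed hysteroscopy to laparoscopy is also unsettled, and it affects both the crossover proportion in Table 2 and the category for LTS after an Essure attempt.

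**Working it through.** The plan states no failure rate, event count or sample size on this point, so there is no figure to reproduce. The check is a trace of the definitions, followed by arithmetic on assumed rates.

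**Trace.** Take a woman who selected Essure and whose hysteroscopy stopped before an insert was in the channel.

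- **No laparoscopy follows.** She meets neither FAS threshold and is in the Safety Analysis Set only. Under SAP 6.6.2 her AEs and her failure enter no rate table.
- **Laparoscopy follows; Day 0 is the hysteroscopy.** She enters the FAS by the puncture. By the SAP 2 definition she made no Essure attempt, so SAP 5.2 appears to make her LTS. Her hysteroscopy harms start on or after Day 0 and count as treatment-emergent LTS events (SAP 6.4).
- **Laparoscopy follows; Day 0 is the laparoscopy, on a later date.** She again appears to be LTS, but the earlier harms precede Day 0 and are not treatment-emergent.
- **Laparoscopy follows; group taken from the method selected.** She is an Essure woman in the FAS and counts as a crossover.

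SAP 4.4.2 sets Day 0 at the initial procedure, but does not say whether a hysteroscopy stopped before loading is that procedure. On the second and third paths she is missed both by the crossover proportion and by the category for LTS after an Essure attempt.

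**Illustrative size.** Every rate here is an assumption, except the anticipated 2:1 ratio (SAP 4.1).

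- f = share of started hysteroscopies stopped before loading: 1% to 5%
- q = day-0 AE risk once loaded: 2%
- qa = day-0 AE risk in the stopped women: 5% to 20%
- g = procedure failure after loading: 5%
- c = share of stopped women who go on to laparoscopy: 50% to 100%

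Day-0 AE incidence over all started hysteroscopies = (1 − f)·q + f·qa, against q = 2.00% in the FAS:

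- f = 1%, qa = 5%: 0.99 × 2% + 0.01 × 5% = 2.03%
- f = 5%, qa = 20%: 0.95 × 2% + 0.05 × 20% = 2.90%

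The gap is 0.03 to 0.90 percentage points.

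Procedure failure over all started = f + (1 − f)·g, against g = 5.0% in the FAS:

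- f = 1%: 1% + 0.99 × 5% = 5.95%
- f = 5%: 5% + 0.95 × 5% = 9.75%

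Share of the LTS group made up of relabelled women, per 100 hysteroscopies and 200 LTS women = 100·f·c / (200 + 100·f·c):

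- f = 1%, c = 50%: 0.5 / 200.5 = 0.25%
- f = 5%, c = 100%: 5 / 205 = 2.44%

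**The case against.** **The threshold is deliberate.** The objectives define an attempt by the insert in the channel, the protocol and SAP agree, and this is a mandated surveillance study of the device. Moving FAS entry to scope introduction would override the stated objectives and change the population used for propensity matching. It would also add same-session converts to the Essure denominator and censor them at Day 0 (SAP 4.3, 6.1.3), leaving them almost no time to have a long-term event. With 4% such women, an illustrative 10% chronic pain incidence would fall to 0.96 × 10% = 9.6%. This stands, and it is why the FAS should not be redefined.

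**The women leave a trace.** Reasons for exclusion from the analysis populations are tabulated (SAP 6.1.1), all subjects with an AE are listed (SAP 6.5.1), and failed primary procedures and conversions will be reported (protocol 9.2.2.3). It would be wrong to say that they vanish. None of these outputs, however, is specified as a rate by group.

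**A reader might infer that the rule always favors Essure.** The documents do not support this. LTS harms before the puncture are also outside the FAS, and LTS is typically done under general anesthesia (protocol 3.5).

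**A reader might infer that these events are certainly charged to LTS.** No section says so. The word attempted in SAP 5.2 points that way. Allocation by decision (SAP 4.4.2), initial allocation at index (SAP 4.5.1), the method selected at index (reliance set, SAP 5.1) and the initial index event (SAP 6.4.5) point to the method chosen or leave the matter open.

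**A reader might infer a large understatement of the surgery endpoint.** Take an assumed 10% incidence in the other Essure women, with 1% to 4% stopped before loading and all of those later having LTS. The total would be 0.99 × 10% + 1% = 10.9% to 0.96 × 10% + 4% = 13.6%. That is a ceiling on invented inputs. If half had LTS and the rest no surgery, it is 9.9% + 0.5% = 10.4% to 9.6% + 2.0% = 11.6%. The excess is the replacement sterilization itself, not added injury.

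**Conclusion.** The concern holds in a limited form. Two facts are plain on the text: the FAS entry points are not equivalent, and no AE table is assigned to the Safety Analysis Set. A woman whose hysteroscopy stops before loading and who has no later qualifying procedure therefore contributes to no AE rate in either group. For a woman who goes on to laparoscopy, the group and index date are not stated; the most literal reading makes her LTS, but that is an inference.

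The size cannot be established from the documents. The ranges worked out above rest wholly on assumed rates and show only an order of magnitude. The effect falls on day-0 procedure-related AEs, procedure failures and conversions. Chronic pain, bleeding and autoimmune endpoints should be little affected, and the matched primary analysis is not undermined. The remaining gap is worth closing because the study exists to report safety by procedure and the set and the data are already in place.

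**What to change.** 1. In SAP 6.6.2, add tables on the Safety Analysis Set for summary AEs, SAEs, procedure-related AEs (including those related to hysteroscopy) and procedure failure or conversion, grouped by the procedure selected for the visit. This also brings in LTS women whose procedure stopped before the puncture, so the two groups are counted from the same point.
2. In SAP 4.4.2 and 5.2, state the group and index date for a woman converted before an insert is loaded, and whether she counts in the crossover proportion and in the category for LTS after an Essure attempt.
3. Leave the FAS definition and the matched primary analysis unchanged.

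The cost is SAP wording and a few extra tables. The Essure procedure fields are already listed in Table 2, so no new data are needed. The drawback is that the added tables include women never exposed to the insert, so they describe the intended procedure rather than the device. A footnote giving the number of such women in each group would make that clear.

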#### **Adjusted full analysis set**

Same as Full Analysis Set, but based on propensity score confounder-adjusted population, see Section [6.5.1](#).

#### **Reliance set**

A subject will be included in the reliance set if she has been told to rely on the sterilization method selected at the index event.

## Adjusted reliance set

Among the propensity score confounder-adjusted population, a subject will be included if both she and her matched partner are included in the Reliance Set.

